8 REPORTING PROCESS FOR ADVERSE EVENTS, ADVERSE DEVICE EFFECTS AND DEVICE DEFICIENCIES

8.1 Definitions

All definitions are according to the EN ISO 14155:2011 standard.

8.1.1 Adverse event (AE)

Any untoward medical occurrence, unintended disease or injury, or untoward clinical signs (including abnormal laboratory findings) in subjects, users or other persons whether or not related to the investigational medical device.

NOTE 1 This definition includes events related to the investigational medical device or the comparator.

NOTE 2 This definition includes events related to the procedures involved.

NOTE 3 For users and other persons, this definition is restricted to events related to investigational medical devices.

8.1.2 Adverse device effect (ADE)

Adverse device effect is an adverse event related to the use of an investigational medical device.

NOTE 1 This includes any adverse event resulting from insufficiencies or inadequacies in the instructions for use, the deployment, the implantation, the installation, the operation, or any malfunction of the investigational medical device.

NOTE 2 This definition includes any event resulting from use error or from intentional misuse of the investigational medical device.

8.1.3 Device deficiency (DD)

A device deficiency is an inadequacy of a medical device with respect to its identity, quality, durability, reliability, safety or performance.

NOTE Device deficiencies include malfunctions, use errors, and inadequate labelling.

8.1.4 Serious adverse event (SAE)

A serious adverse event is any adverse event that:

- 1) led to a death,
- 2) led to a serious deterioration in the health of the subject that either resulted in
 - a) a life-threatening illness or injury, or
 - b) a permanent impairment of a body structure or a body function, or
 - c) in-patient hospitalization or prolonged hospitalization, or
 - d) medical or surgical intervention to prevent life-threatening illness or injury or permanent impairment to a body structure or a body function,
- 3) led to fetal distress, fetal death or a congenital abnormality or birth defect

NOTE Planned hospitalization for a pre-existing condition, or a procedure required by the CIP, without serious deterioration in health, is not considered a serious adverse event.

8.1.5 Unanticipated adverse device effect (UADE)

An unanticipated serious adverse device effect is a serious adverse device effect which by its nature, incidence, severity or outcome has not been identified in the risk analysis report (for the investigational device or its comparator).

8.2 Reporting process for adverse events

8.2.1 Unanticipated Adverse Device Effects

Unanticipated adverse device effects (UADEs) must be reported directly to the clinical center's reviewing IRB and the Sponsor, Cochlear Americas, within 10 working days of knowledge of the event, or as dictated by the specific IRB policy, whichever is sooner. Information regarding the UADE will be recorded on the *Unanticipated Adverse Device Effect Report*, provided with the CRFs for the study.

8.2.2 Adverse Event Follow-up

All AEs must be followed until resolution, or the condition stabilizes. The Investigator is responsible to ensure that follow-up includes any supplemental investigations as may be indicated to elucidate as completely as possible the nature and/or causality of the AE. This may include additional laboratory tests or investigations, or consultation with other health care professionals. Cochlear or its designee may request that the Investigator perform or arrange for the conduct of supplemental measurements and/or evaluations. AE follow up information will be recorded using a *Follow Up to a Previously Reported Adverse Event Questionnaire*, provided with the CRFs for the study.

8.2.3 Sponsor's Responsibilities

All AE, DD and SAEs will be reported in the Annual Progress Report (APR) to FDA in accordance with the IDE regulation [FDA 21 CFR Part 812.150(b)(5)].

All unanticipated adverse device effects (UADEs) will be reported to FDA within 10 calendar days of the event in accordance with FDA 21 CFR Part 812.46(b) and 812.150(b)(1).

Cochlear Americas or its designee will notify all participating Investigators of any new information that alters the current risk-benefit assessment of the study device or that would be sufficient to consider changes in management of the Nucleus cochlear implant or in the overall conduct of the trial.

8.3 Data Monitoring Committee

No DMC will be established.

9 STUDY COMPLETION

9.1 Completed Subjects

Each subject in the study will be considered completed when all assessments through 12 months post-activation have been performed in accordance with the study protocol. To be considered a primary endpoint success at 6 months postactivation, subjects must retain their originally implanted device.

9.2 Discontinued Subjects

Any subject may voluntarily discontinue the study at any time without prejudice. The Investigator may discontinue a subject from the study at any time if (s)he considers that remaining in the study compromises the subject's health or the subject is not sufficiently cooperative. In either event, reason(s) for discontinuation should be recorded on a study withdrawal form, provided as part of the CRFs for the study.

Possible reasons for study discontinuation include the following:

- AE necessitating discontinuation from the study
- The subject is lost to follow-up
- Voluntary decision to withdraw consent made by the subject⁹
- Investigator decision¹⁰

⁹ Withdrawal of consent is defined as the subject's voluntary decision to revoke consent to continue participation in the study.

¹⁰ Subject withdrawal from the study is defined as an Investigator decision. The Investigator may elect to withdraw a subject from the study at any time if he/she considers that remaining in the study compromises the patient's health or if the Investigator considers the subject lost to follow-up.

- Other reason

In case of a subject lost-to-follow-up, the Investigator must attempt to contact the subject (or relative/family contact) by phone, email or letter at least three times. If attempts are unsuccessful, the 'subject withdrawal' form is to be completed in the study file and reported, as appropriate, in required reports to the Sponsor, IRB and FDA.

9.3 Premature Study Termination

The Sponsor reserves the right to discontinue the study for any safety, ethical or administrative reason at any time. Subjects already implanted with the device being studied will continue to be supported, independent of any decision made about study continuation.

10 STATISTICAL CONSIDERATIONS

All subjects who are recruited to the clinical investigation will constitute the intention-to-treat (ITT) population for the purposes of safety evaluation. Only subjects implanted with the CI532 and completed per the protocol will be considered as the completed cases (CC) population and per protocol (PP).

As this is a feasibility clinical investigation, there have been no formal power or sample size estimations performed for the primary objectives. The intent of the proposed investigation is to establish preliminary safety and effectiveness data. There are no pass/fail criteria to be applied to the results of the clinical investigation.

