4.6 Investigation schedule

Table 1: Investigation schedule

Procedure	Pre-op	Surgery	Activation	3 months post-activation	6 months post-activation	12 months post-activation
Medical history	x					
X-ray		x				
Impedances			x	x	x	x
T/C Levels			x	x	x	x
Speech Perception Testing	x			x	x	x
Unaided Audiogram	x		x	x	x	x
SSQ	x				x	
GBI					x	
Surgical Questionnaire		x				
Adverse Events		x	x	x	x	x

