4.7.2 Exclusion Criteria

1. Evidence of hearing loss prior to 5 years of age
2. Sensorineural severe-to-profound hearing loss greater than 20 years at ≥ 2 kHz and above
3. Simultaneous bilateral cochlear implantation or prior cochlear implantation in the ear to be implanted
4. Medical or psychological conditions that contraindicate undergoing general anaesthesia or surgery
5. Ossification, malformation or any other cochlear anomaly, such as common cavity, that might prevent complete insertion of the electrode array, as confirmed by medical examination
6. Hearing impairment due to lesion or neuropathy of the acoustic nerve, VIII nerve or central auditory pathway
7. Active middle-ear infection
8. Tympanic membrane perforation
9. Unrealistic expectations on the part of the subject, regarding the possible benefits, risks, and limitations that are inherent to the surgical procedure(s) and prosthetic devices as determined by the Investigator
10. Unwillingness or inability of the candidate to comply with all investigational requirements as determined by the Investigator
11. Patients with existing CSF shunts or drains, existing perilymph fistula, skull fracture or CSF leak
12. Patients with recurrent episodes of bacterial meningitis

² If it is more than 90 days past the date of the Candidacy Evaluation, candidacy needs to be reconfirmed by repeating hearing threshold test measures at 250 and 500Hz. Any changes observed will need to be reviewed in consultation with the Sponsor prior to surgery occurring. If candidate is not currently aided in the ear to be implanted, documentation of previous hearing aid trial is required.

³ As judged by the investigator i.e. able to complete the speech perception assessments tasks and questionnaires.

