4.7.3 Number of subjects required

The proposed study is designed to collect safety and efficacy data associated with CI532 cochlear implantation and the feasibility of fitting of the acoustic component postoperatively in adults. The protocol describes a feasibility study within a single site and a limited number of subjects (up to 10 subjects). Based on the data collected in IDE G120234, assuming the observed mean and standard deviation for each endpoint are representative of the corresponding values for the population, it was determined that a minimum of 23 evaluable subjects would provide at least 90% power for a hypothesis test of superiority at the one-sided 0.025 alpha level. Allowance of 10% to account for possible attrition brings the sample size to 25 subjects to be recruited into the study and implanted. The planned sample size of up to 10 subjects will not provide adequate power for the primary efficacy endpoints hence the proposal for a feasibility study design.

The following general assumptions have been made:

- Paired t-tests
- One-sided 0.025 or 0.05 alpha levels
- Assumed distribution for population (mean, SD) based on IDE G120234
- Desire for 80% or 90% power

Power for the primary test metric AzBio Sentences in SWN under a variety of assumptions is provided below.

Scenario	Minimum Evaluable Sample Size
One-sided 0.025 alpha, 80% power	18
One-sided 0.025 alpha, 90% power	23
One-sided 0.05 alpha, 80% power	16
One-sided 0.05 alpha, 90% power	20

Subject enrollment is estimated to take three months to recruit up to 10 subjects at a single investigational site. The enrollment period may be extended if required.

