4.7.5 Subject replacement

The total number of subjects proposed for this clinical investigation is up to 10. If a subject withdraws pre-operatively, they will be replaced by a newly recruited subject who meets the selection criteria for participation.

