4.7.6 Point of enrollment

Subjects are recruited to the study by the investigators usually during the course of medical consultation. Subjects will be sequentially enrolled once Cochlear Americas receives a properly executed Informed Consent form and has approved the preoperative candidacy evaluation.

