10.2 Safety Measurements

No formal statistical hypothesis will be tested. The number and percent of patients with adverse events will be reported and tabulated, including the number and percentage of tip fold overs. Adverse events will be summarized by event type, severity, seriousness, as well as relatedness to the device and implant procedure. Since the proposed study involves a limited number of subjects, group analyses are not planned.

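### The safety population is all recruited subjects, so a subject who leaves before surgery would count in the adverse event denominator

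*Protocol*

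**What the plan says.** Section 10 assigns one population to safety: "All subjects who are recruited to the clinical investigation will constitute the intention-to-treat (ITT) population for the purposes of safety evaluation". The only set tied to implantation is the completed-cases/per-protocol set. That set requires both a CI532 and completion, and it is not assigned to safety.

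Section 4.7.6 places recruitment before surgery: "Subjects are recruited to the study by the investigators usually during the course of medical consultation". Enrolment is also pre-operative: "Subjects will be sequentially enrolled once Cochlear Americas receives a properly executed Informed Consent form and has approved the preoperative candidacy evaluation". Section 4.7.3, describing a fully powered study, names recruitment and implantation as two steps: "brings the sample size to 25 subjects to be recruited into the study and implanted". Section 4.7.5 foresees exit between them: "If a subject withdraws pre-operatively, they will be replaced by a newly recruited subject".

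For reporting, section 10.2 says: "The number and percent of patients with adverse events will be reported and tabulated, including the number and percentage of tip fold overs". It adds that events will be summarised by relatedness to the device and to the implant procedure. Section 4.3.1 makes the frequency of medical/surgical and device-related events, set against the approved labelling, a primary safety endpoint. Section 11 reports fold-overs confirmed on the X-ray taken during surgery. In section 4.6 ("Table 1: Investigation schedule"), the X-ray falls at surgery and adverse event collection runs from surgery onward.

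**The concern.** A safety percentage should rest on the subjects who were exposed to the risk. Here the exposure is the implant operation. A subject recruited at a consultation who withdraws before the operation has no exposure and no scheduled safety assessment, but section 10 counts that subject as part of the safety population. Nothing in the protocol takes a replaced subject out again.

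The result would be a diluted rate for events that only operated subjects can have. The dilution runs one way, towards making the device look safer. It would affect the comparison with labelling, where frequency is one of the three named dimensions. Section 5 says the results may support a randomised multicentre investigation, so later readers should be able to tell what each percentage is a percentage of.

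**Working it through.** The protocol states no figure to reproduce here. The check is a reading of the text followed by simple arithmetic.

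**Step 1. Can the recruited outnumber the operated?** Yes. Sections 4.7.6 and 4.7.5 together allow a subject to be recruited, withdraw before surgery and be replaced. The ITT definition in section 22.2 does not narrow the set, because it speaks of groups allocated by randomisation and this study has one arm.

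**Step 2. What can a never-operated subject contribute?** One to the denominator, and nothing to the numerator for fold-overs or for events related to the device or the implant procedure.

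**Step 3. Size.** Inputs: 10 operated subjects (the planned maximum, sections 4.7.3 and 4.7.5) and w pre-operative withdrawals. The protocol does not give w; 0 to 2 is assumed. With x operated subjects having the event:

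- operated denominator: x / 10
- recruited denominator: x / (10 + w)
- ratio: 10 / (10 + w)

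| w | Recruited | Ratio | 1 event | 2 events |
|---|---|---|---|---|
| 0 | 10 | 1.00 | 10.0% | 20.0% |
| 1 | 11 | 0.91 | 9.1% | 18.2% |
| 2 | 12 | 0.83 | 8.3% | 16.7% |

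For one event the shift is 10.0 − 9.1 = 0.9 points or 10.0 − 8.3 = 1.7 points. For two events it is 20.0 − 18.2 = 1.8 points or 20.0 − 16.7 = 3.3 points. With no event the percentage is 0% throughout, but the exact upper 95% limit falls from 30.8% (0/10) to 28.5% (0/11) or 26.5% (0/12).

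**Step 4. Comparison with sampling error.** The exact (Clopper-Pearson) 95% interval is 0.3% to 44.5% for 1/10 and 2.5% to 55.6% for 2/10. The shift is small beside either.

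**Step 5. Direction for all adverse events.** Section 7.11 has any adverse event during the investigation reported, so a subject who withdraws before surgery could still have one. One event among 10 operated plus one in a single withdrawn subject gives (1 + 1)/(10 + 1) = 18.2%, above 1/10 = 10.0%. The downward direction is therefore certain only for events that require the operation.

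**The case against.** The strongest reply is that replacement under a fixed total already settles the matter. The study is capped at up to 10 subjects, and a withdrawn subject is replaced. If the withdrawn subject still counted, replacement at full enrolment would exceed the cap. On that reading the withdrawn subject gives up the place, and the counted set is those who go to surgery. This is reasonable, but no section says it, and section 10 says *recruited*. It shows an ambiguity and does not remove the literal rule.

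Three stronger readings are tempting, and the protocol does not support them:

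- **That it promises diluted percentages of device-related and procedure-related events.** Section 10.2 promises a number and percent for patients with adverse events and for fold-overs. Relatedness is only to be summarised. The dilution applies if that summary, or the comparison with labelling, is given as percentages.
- **That the fold-over percentage will be diluted.** Section 11 ties fold-overs to the intraoperative X-ray, which makes X-rayed subjects the natural denominator. It does not state one, so the literal reading stays possible but is the less likely one.
- **That the candidacy recheck is a second foreseen route out.** Footnote 2 to the eligibility criteria says "If it is more than 90 days past the date of the Candidacy Evaluation, candidacy needs to be reconfirmed", with changes reviewed with the sponsor. It states a recheck and no exit. Only section 4.7.5 foresees withdrawal before surgery.

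It is also fair to say that nothing formal depends on this. Section 10.2 tests no safety hypothesis, section 10 sets no pass/fail criterion, and with counts beside percentages in a study this small a reader told how many were operated on can recompute any rate.

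**Conclusion.** The point holds as a minor defect. Section 10 fixes a safety population that is wider than the subjects exposed to surgery, and the protocol foresees the circumstance in which the two differ. An analysis plan that used operated subjects would be departing from the protocol's words.

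On the assumption of 10 operated subjects and one or two pre-operative withdrawals, percentages of events that require the operation would be multiplied by 0.91 or 0.83. For one or two events that is a shift of 0.9 to 3.3 percentage points, and it vanishes if nobody withdraws before surgery. No conclusion that the study is set up to draw would change. Keeping subjects converted to another device in the safety population, as the present wording does, is sound.

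**What to change.** In section 10, define the safety set as all subjects in whom implant surgery was started, including those converted to another device during the operation. State that the tip fold-over percentage uses all subjects with an attempted CI532 insertion as its denominator, again including conversions. List pre-operative withdrawals, and any adverse events they had, separately.

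The cost is one or two sentences. If anyone withdraws before surgery, the reported percentages of implant-related events will be slightly higher than under the present wording, and any pre-operative adverse events in withdrawn subjects move from the main table to the separate listing. No data are lost and no further data collection is needed.

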10.1 Efficacy Measurements

At a minimum, individual data will be tabulated and summarized for all measures to establish the proportions of those subjects showing improvement, no change, and decrement in performance.

The efficacy objectives include:

- a) To understand if subjects implanted with the CI532 can retain low frequency thresholds and be fit with the acoustic component

Audiometric data will be collected and acoustic fittings will be tracked at each follow up time point. For those fit with the acoustic component, outcomes will be assessed with and without the acoustic component.

- b) To understand if implantation with the CI532 results in improved postoperative speech perception outcomes in both quiet and noise when using the best unilateral listening condition

Device efficacy will be evaluated by comparisons of group and individual performance pre- and postoperatively at 3, 6, and 12-months post-activation. Performance benefits are change in scores pre- to post-operatively:

- Gain in speech recognition in quiet on CNC words (% correct)
- Gain in speech recognition in noise on AzBio Sentences (% correct)

c) To understand if implantation with the CI532 results in improved patient reported hearing performance and health utility

Scores from the SSQ obtained postoperatively will be compared with those obtained preoperatively, prior to implantation. The SSQ will act to provide a measure of hearing performance as perceived by the subjects. The GBI will provide a measure of change in health status as a result of cochlear implantation. Since the GBI is structured as a post-intervention (change) metric, there will be no preoperative measures derived for comparison with postoperative scores.

10.2 Safety Measurements

No formal statistical hypothesis will be tested. The number and percent of patients with adverse events will be reported and tabulated, including the number and percentage of tip fold overs. Adverse events will be summarized by event type, severity, seriousness, as well as relatedness to the device and implant procedure. Since the proposed study involves a limited number of subjects, group analyses are not planned.

10.3 Baseline Characteristics

The characteristics of the study group will be presented descriptively. Quantitative variables such as age will be presented with mean, standard deviation, median, minimum and maximum and 95% CI. Qualitative variables such as age or gender will be presented as percentages and observed frequencies. If differences in outcome are found for subgroups defined by baseline age or gender, analyses will be performed to explore the possible role of other baseline characteristics to explain the results.

10.4 Missing Data

All efforts will be put forth to ensure near complete follow-up, with particular focus on the assessment of the primary outcomes and occurrence of adverse events. A reminder of subject follow-up due date will be provided to participating centres to facilitate scheduling of the follow-up visit.

In the event a subject is withdrawn prior to the six month post-activation assessment, the analysis of the primary endpoint will involve imputing the last data point captured (candidacy, activation or 3 months post-activation) for the six month post-activation assessment. The p-value for the primary statistical hypothesis tests will be calculated using this imputation to understand the impact of missing data on the primary results.

11 RISKS AND BENEFITS OF THE STUDY DEVICE AND CLINICAL INVESTIGATION

For this clinical investigation, safety will be defined as freedom from device or procedure-related adverse events compared to the commercially available Cochlear Nucleus CI24RE. Additionally, the number and percentage of tip fold overs as confirmed by intraoperative x-ray will be reported.

